2.2 Co-primary endpoint

- Ambulatory function: Preserved ability to walk measured by EQ-5D-5L, see Appendix B.

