The PRO-CTCAE® items and information herein were developed by the Division of Cancer Control and Population Sciences in the NATIONAL CANCER INSTITUTE at the NATIONAL INSTITUTES OF HEALTH, in Bethesda, Maryland, U.S.A. Use of the PRO-CTCAE® is subject to NCI's Terms of Use.

Health Questionnaire

English version for the UK

Under each heading, please tick the ONE box that best describes your health TODAY.

MOBILITY

I have no problems in walking about	
I have slight problems in walking about	
I have moderate problems in walking about	
I have severe problems in walking about	
I am unable to walk about	

SELF-CARE

I have no problems washing or dressing myself	
I have slight problems washing or dressing myself	
I have moderate problems washing or dressing myself	
I have severe problems washing or dressing myself	
I am unable to wash or dress myself	

USUAL ACTIVITIES (e.g. work, study, housework, family or leisure activities)

I have no problems doing my usual activities	
I have slight problems doing my usual activities	
I have moderate problems doing my usual activities	
I have severe problems doing my usual activities	
I am unable to do my usual activities	

PAIN / DISCOMFORT

[figure not shown]
I have no pain or discomfort	
I have slight pain or discomfort	
I have moderate pain or discomfort	
I have severe pain or discomfort	
I have extreme pain or discomfort	

ANXIETY / DEPRESSION

I am not anxious or depressed	
I am slightly anxious or depressed	
I am moderately anxious or depressed	
I am severely anxious or depressed	
I am extremely anxious or depressed	

- We would like to know how good or bad your health is TODAY.
- This scale is numbered from 0 to 100.
- 100 means the best health you can imagine.
0 means the worst health you can imagine.
- Please mark an X on the scale to indicate how your health is TODAY.

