2. To investigate if there is a difference in pain response, weight, primary treatment site re-irradiation, quality of life and overall survival in patients treated with esophagus-sparring radiotherapy compared to patients receiving standard treatment.

3. To describe the dose-response relationship for the esophagus in the palliative dose spectrum.
4. To investigate if esophagus-sparring radiotherapy will increase other toxicities compared to standard radiotherapy.

Primary endpoints

Co-primary endpoints are

- a. Peak patient reported dysphagia (PRO-CTC-AE version 1) within the first five week after treatment start.
- b. Ability to walk, measured by the mobility dimension of the EQ-5D-5L questionnaire.

Secondary endpoints

- Quality of life, measured by EORTC-QLQ-C30 and EQ-5D-5L
- Nausea and dyspepsia measured by PRO-CTC-AE Version 1.0
- Treatment site pain response measured by International Consensus Pain Response Endpoints (ICPRE)
- Patient reported toxicity reported in PRO-CTC-AE-Version 1.0 “Other symptoms” section
- CTC-AE* Version 5: Cough, dyspnea, dyspepsia, dysphagia, hoarseness, oropharyngeal pain
- Changes in weight
- Consumption of corticosteroids, antacids and antiemetics
- Treatment site re-irradiation rate
- Hospitalization rate
- Overall survival

*Registered from patient no. 107

Trial design

The trial is designed as a phase III, randomized, single-blind clinical trial, clinicaltrials.gov ID No. NCT051098.

The trial is performed in a public health care system including two academic cancer centers treating MSCC. The individual centers are started at different times due to logistics. Patients are randomized 1:1 to either esophagus-sparring treatment or standard treatment. Patients are followed actively for 9 weeks after treatment start. Dysphagia, nausea and dyspepsia from the NCI PRO-CTC-AE Version 1.0 library and treatment site pain (Numeric Pain Rating Scale) are reported daily for 5 weeks and subsequently weekly for 4 weeks. Quality of life (EQ-5D-5L and QLQ-C30), use of medication (glucocorticoid, antiemetic, analgesic) and weight are reported weekly for 9 weeks, **Table 1**.

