We assume that we can decrease maximum esophageal dose from 30 Gy to 10 Gy and that this will result in a 50% decrease in risk of early esophageal toxicity. We want to conduct a phase III trial with 1:1 randomization between standard VMAT and experimental esophageal VMAT. Prior data (2) indicate that the rate of early esophageal toxicity with standard VMAT is 0.6. If the true early esophageal toxicity rate in the esophagus sparing VMAT arm is 0.3, conventional power calculation indicates that we would need to include 62 patients in each arm, to be able to reject the null hypothesis that the toxicity rates for experimental and control arms are equal with a probability (power) of 0.9. The Type I error probability associated with the test of this null hypothesis is 0.05 and calculations are performed assuming Fisher's exact test. However, with this patient population we anticipate high rate of heterogeneity, and we need to account for loss of follow-up due to patients dying early or being too frail. We increase the study size to 100 patients in each arm to account for these challenges. Patients will be stratified according to fractionation scheme and treating center.

Ambulatory function as a co-primary endpoint

We wish to demonstrate that the improvement in esophageal toxicity does not come at a price of reduced effect of the radiation. As a prioritized secondary endpoint, we choose ambulatory function (preserved ability to walk) measured on a 4-point scale. We assume that the conventional arm follows the distribution of the SCORAD trial and test our ability to detect a difference from an assumed inferior experimental arm in terms of ambulatory function, see Table 2.

If the underlying “true” distribution on ambulatory grades is as depicted in the table and we assume 66 patients per arm are evaluable, we find that 84% of simulated trials would lead to statistically significant differences detected with a Wilcoxon rank sum test for comparing the trial arms. In other words, the power of the trial is enough to detect a deterioration according to the able, which would lead to rejection of the experimental treatment.

The power of ESO-SPARE is enough to detect a difference in ambulatory function as seen in Table 2

	Conventional arm	Experimental arm
Grade 1: Ambulatory without the use of walking aids	22	11
Grade 2: Ambulatory with walking aids	44	32
Grade 3: Unable to walk	26	37
Grade 4: Absence or flicker of motor power in any muscle group	8	20

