Table 2: Distribution of ambulatory function. The conventional arm follows the SCORAD trial (Hoskin et al., 2019).

Recruitment, withdrawal, and follow-up

Enrollment, intervention, allocation, follow-up, and data analysis will be summarized in a CONSORT diagram in accordance with CONSORT 2010 guidelines (4)

Statistical principles

Confidence intervals and P values

Level of significance: $p < 0.05$ with no adjustment for multiplicity. Confidence intervals are reported at 95 % limits (bound by zero) and calculated by the binominal distribution for rates and as per Kaplan-Meier method for time-to-event analyses.

Analysis

We will report our data in accordance with the CONSORT 2010 guidelines including the CONSORT Patient-Reported Outcome (PRO) extension (4,5) .

Analyses will be performed per-protocol for all patients who have received any study treatment.

Primary analysis of NCI-PRO-CTC-AE toxicity will only include weeks where ≥ 3 days questionnaires are completed.

Primary analysis of EQ-5D-5L and EORTC-QLQ-C30 will only include completed questionnaires.

All CTC-AE and PRO-CTC-AE grades will be reported.

Missing data will be described in detail, see missing data section.

A. Co-primary endpoints

1. Peak dysphagia (difficulty swallowing) measured by NCI-PRO-CTC-AE within 5 weeks after start of radiotherapy (daily measurements).

PRO-CTC-AE responses are scored from 0 to 4, with 0 representing "None" and 4 representing "Very severe". For each patient the peak value within 5 weeks after start of radiotherapy (daily measurements) will be included in the analysis. Difference in scores between treatment arms will be compared using Wilcoxon rank-sum test.

2. Ambulatory function measured by EQ-5D-5L mobility dimension at 9 weeks after start of radiotherapy.

EQ-5D-5L measures individual generic health status using 5 dimensions: mobility, self-care, usual activities, pain/discomfort, and anxiety/depression. Each dimension has 5 levels depending on the severity of symptoms, with 1 representing “No problems” and 5 representing “Extreme problems”. Difference in scores between mobility dimension treatment arms will be compared using Wilcoxon rank-sum test.

B. Severity of dysphagia, nausea and dyspepsia measured by NCI-PRO-CTC-AE [Time Frame: Week 1-9 after start of radiotherapy (repeated measurement)].

CTC-AE responses are scored from 0 to 4, with 0 representing “None” and 4 representing “Very severe”.

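### The co-primary is named ability to walk, but the SAP tests only a five-level mobility score, to which the stated 84% power does not apply and which gives no estimate of who can walk

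*SAP*

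**What the plan says.** Protocol 2.2 gives the co-primary endpoint as "Ambulatory function: Preserved ability to walk measured by EQ-5D-5L, see Appendix B". The SAP, under Primary endpoints, has "Ability to walk, measured by the mobility dimension of the EQ-5D-5L questionnaire". Neither gives a cut-off for being able to walk or a definition of preserved.

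Both documents justify the sample size for this endpoint (protocol 3.4; SAP, Ambulatory function as a co-primary endpoint) with the words "we choose ambulatory function (preserved ability to walk) measured on a 4-point scale". That scale starts at "Grade 1: Ambulatory without the use of walking aids" and has two walking grades and two non-walking grades. With 66 evaluable patients per arm and a Wilcoxon rank-sum test, the stated power is 84%. A deterioration like the one tabulated would lead to rejection of the experimental treatment.

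The analysis itself (SAP, Analysis A.2) is "Ambulatory function measured by EQ-5D-5L mobility dimension at 9 weeks after start of radiotherapy", and: "Difference in scores between mobility dimension treatment arms will be compared using Wilcoxon rank-sum test". The SAP's Analysis summary table repeats this. In the EQ-5D-5L questionnaire appended to the protocol, the mobility item has five answers, and only the last, "I am unable to walk about", means loss of walking.

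**The concern.** The four-grade scale puts the walk/no-walk boundary in the middle. The analysed item puts it at the very end: four levels separate degrees of difficulty among walkers and one level holds everyone who cannot walk. The rank-sum result then depends heavily on how walkers grade themselves, which is not what the endpoint's name describes.

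The SAP plans no able/unable proportion, no between-arm difference or confidence interval for walking, and no use of walking status at treatment start. Item O of the analysis list mentions ability to walk, but only in a correlation with target coverage and without defining it.

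This endpoint is the safety counterweight to sparing the esophagus, which by protocol 6.4 may compromise target dose. A non-significant rank test could be reported as walking preserved, or a significant one as walking lost, with neither shown.

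**Working it through.** **Inputs from the documents.** Table 2 of the SAP (Table 1 of the protocol), grades 1 to 4: conventional 22/44/26/8%, experimental 11/32/37/20%. Evaluable patients: 66 per arm. Significance level 0.05, taken as two-sided because sidedness is not stated.

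**Derived.** Unable to walk (grades 3+4): 26 + 8 = 34% v 37 + 20 = 57%. Able to walk: 66% v 43%.

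**Method.** Multinomial simulation of trials, with a tie-corrected Wilcoxon test. Beside the power stands θ = P(experimental worse) + ½P(tie) for one patient drawn from each arm, where 0.5 means no difference.

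**1. The plan's own figure.** For the four-grade table:

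θ = (0.32×0.22 + 0.37×0.66 + 0.20×0.92) + ½(0.11×0.22 + 0.32×0.44 + 0.37×0.26 + 0.20×0.08) = 0.4986 + 0.1386 = 0.637.

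Simulated power is 83%, so the stated 84% reproduces. It belongs to the four-grade scale.

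**2. Able v unable (levels 1-4 v 5), 66 per arm.** Pooled z-test:

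- Standard error under no difference: √(2×0.545×0.455/66) = 0.0867
- Standard error under the alternative: √((0.66×0.34 + 0.43×0.57)/66) = 0.0843
- Power = Φ[(0.23 − 1.96×0.0867)/0.0843] = Φ(0.71) = 76%

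Simulation of the same comparison gives 75%; Fisher's exact test gives 69%. None of these depends on how walkers are spread over levels 1-4.

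**3. The SAP's five-level test with the same 34% v 57% unable.** The documents give no distribution over levels 1-4, so every split below is an assumption.

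| How the walkers are spread | Conventional, levels 1-5 (%) | Experimental, levels 1-5 (%) | θ | Power |
|---|---|---|---|---|
| Walkers worsen as in Table 2 (grade 1 over levels 1-2, grade 2 over levels 3-4) | 11/11/22/22/34 | 5.5/5.5/16/16/57 | 0.626 | 76-77% |
| Walkers split alike in both arms | 16.5/16.5/16.5/16.5/34 | 10.75/10.75/10.75/10.75/57 | 0.615 | 68% |
| Loss half from level 4, half from all walking levels | 16/17/17/16/34 | 13.2/14/14/1.8/57 | 0.587 | 45% |
| Loss only from the worst walkers | 16.5/16.5/16.5/16.5/34 | 16.5/16.5/10/0/57 | 0.569 | 31% |
| Loss only from the worst walkers, milder cohort | 22/20/14/10/34 | 22/20/1/0/57 | 0.566 | 29% |

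The second row shows the mechanism. With walkers split alike, θ = 0.5 + 0.23/2 = 0.615, which is also the able/unable value. Ranking the walkers then adds variance but no signal, and power falls from 75% to 68%.

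**4. Equal ability to walk (34% unable in both arms), worse scores among walkers only.**

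| Conventional, levels 1-4 (%) | Experimental, levels 1-4 (%) | Significant trials |
|---|---|---|
| 16.5/16.5/16.5/16.5 | 9.9/13.2/19.8/23.1 | 12% |
| 16.5/16.5/16.5/16.5 | 6.6/13.2/19.8/26.4 | 20% |
| 25/20/12/9 | 12/15/20/19 | 29% |
| 25/20/12/9 | 8/12/20/26 | 50-51% |
| 26.4/19.8/13.2/6.6 | 6.6/13.2/19.8/26.4 | 61% |

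The able/unable comparison stays at 5% in all of these.

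**5. Limits of the able/unable comparison.** At 66% v 43% it needs 73 evaluable patients per arm for 80% power and 81 for 84% (81 and 89 with continuity correction). Restricted to patients walking at treatment start, and assuming that 50-80% of them do (33-53 per arm) with the same 66% v 43%, power is 47-67%.

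**The case against.** Three stronger readings are tempting, and the documents do not support them.

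*That the SAP replaced a yes/no protocol endpoint with an ordinal one.* Protocol 3.4 itself uses preserved ability to walk as the label for a graded outcome and plans a Wilcoxon test. Under that plan a shift between two walking grades counts. Protocol 2.2 sets no level-5 cut-off and no restriction to baseline walkers, so levels 1-4 v 5 is a reasonable reading of the name but not a definition the protocol contains.

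*That a deterioration like Table 2 would probably be missed.* Table 2 also worsens the walkers: grade 1 falls from 22 to 11% and grade 2 from 44 to 32%. With the full table carried over to the mobility item, the SAP's test has 76-77% power, no worse than able/unable. The 29-31% results leave the best walkers untouched and nearly or wholly empty the worst walking levels. Table 2 instead halves its best grade, so these are worst cases.

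*That any significant rank-sum result rejects the treatment, even if nobody loses walking.* The sample-size text ties rejection to a deterioration like the table's, which includes the rise from 34 to 57% unable. Worsening among walkers may also be a legitimate sign of reduced radiation effect; whether it should count is a judgement.

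The SAP's description of the top level as extreme problems is generic to all five EQ-5D dimensions and is not a defect. What stands against these objections is that the powered scale is not the analysed scale, and that no planned analysis says how many patients can walk.

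**Conclusion.** The concern holds in a limited form. An ordinal Wilcoxon test was always planned, but the 84% (83% on recalculation) describes a four-grade scale that the SAP does not analyse, and neither document gives a power figure for the five-level item. At 66 per arm with 34% v 57% unable to walk, power on that item was about 29-77% across the assumed splits, below 84% in each, against 69-76% for able/unable. With equal ability to walk, the rank test can still be significant: 12-20% of trials for moderate worsening among walkers, 29-61% for large worsening.

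The ordinal test is not always the weaker one; the gap closes when walkers worsen too. The size of the problem rests on distributions within levels 1-4 that the documents do not give. The conclusion that does not rest on them is that a rank-sum p-value on this item cannot by itself support a statement that walking was preserved or lost.

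**What to change.** Keep the five-level Wilcoxon test as the co-primary test. Add to SAP A.2, as a pre-specified key supporting estimate and not a further co-primary test (the SAP makes no multiplicity adjustment):

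- the proportion able to walk at week 9, defined as mobility levels 1-4 v level 5, with the between-arm difference and 95% CI;
- the same among patients at levels 1-4 at treatment start, as the definition of preserved.

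Base any statement that walking was preserved or lost on these estimates. State in the sample-size section that the 84% refers to the four-grade scale and not to the mobility item.

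The cost is a paragraph of SAP text and one table, from answers already collected at treatment start and weekly. The downsides are that the able/unable comparison ignores gradations among walkers (hence the ordinal test stays), does not restore 84% power, and is less precise among baseline walkers.

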Appendix A

NCI-PRO-CTCAE® CUSTOM SURVEY

Item subset derived from PRO-CTCAE® Item Library Version 1.0

English

Form Created on 17-September-2020

<https://healthcaredelivery.cancer.gov/pro-ctcae/builder.html>

As individuals go through treatment for their cancer they sometimes experience different symptoms and side effects. For each question, please select the one response that best describes your experiences over the past 24 hours...

1a. In the last 24 hours, what was the SEVERITY of your DIFFICULTY SWALLOWING at its WORST?

 None	 Mild	 Moderate	 Severe	 Very severe
----------------------------	----------------------------	--------------------------------	------------------------------	-----------------------------------

2a. In the last 24 hours, how OFTEN did you have NAUSEA?

 Never	 Rarely	 Occasionally	 Frequently	 Almost constantly
-----------------------------	------------------------------	------------------------------------	----------------------------------	---

2b. In the last 24 hours, what was the SEVERITY of your NAUSEA at its WORST?

 None	 Mild	 Moderate	 Severe	 Very severe
----------------------------	----------------------------	--------------------------------	------------------------------	-----------------------------------

3a. In the last 24 hours, how OFTEN did you have HEARTBURN?

 Never	 Rarely	 Occasionally	 Frequently	 Almost constantly
-----------------------------	------------------------------	------------------------------------	----------------------------------	---

3b. In the last 24 hours, what was the SEVERITY of your HEARTBURN at its WORST?

 None	 Mild	 Moderate	 Severe	 Very severe
----------------------------	----------------------------	--------------------------------	------------------------------	-----------------------------------

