For each of the first five weeks, where daily measurements are recorded, the peak value will be used for analysis. Changes in severity score over time (repeated measurement) will be analyzed using Generalized Linear Mixed Models.

C. Duration of dysphagia, nausea and dyspepsia measured by NCI-PRO-CTC-AE [Time Frame: within five weeks after start of RT (daily measurements) and at 6, 7, 8, and 9 weeks].

Duration of toxicity will be presented graphically in separate figures.

For the first five weeks mean duration (days) in each group will be compared using Wilcoxon rank-sum test.

D. Severity of cough, oropharyngeal pain, dyspnea, dysphagia, hoarseness, and dyspepsia measured by CTC-AE (weekly measurements) [Time Frame: Week 1-5 after start of radiotherapy (repeated measurement)].

CTC-AE responses are scored from 0 to 4, with 0 representing “None” and 4 representing “Very severe”.

Changes in severity score over time (repeated measurement) will be analyzed using Generalized Linear Mixed Models.

E. Duration of cough, oropharyngeal pain, dyspnea, dysphagia, hoarseness, and dyspepsia measured by CTC-AE (weekly measurements) [Time Frame: Week 1-5 after start of radiotherapy (repeated measurement)].

Duration of toxicity will be presented graphically in separate figures. Mean duration (weeks) in each group will be compared using Wilcoxon rank-sum test.

F. Demographics: Subject demographics, baseline characteristics and medical history will be summarized descriptively. Generally, range, mean and standard deviation, or median and inter quartile range, will be reported for continuous variables. Frequencies and proportions will be reported for categorical variables.

G. Treatment site pain response [Time frame: weekly, 1-9 weeks after start of RT]:

Only patients with baseline pain will be included in the analysis.

Pain response will be measured by the ICPRE score (6). Possible responses are “Complete response”, “Partial response”, “Pain Progression” and “Intermediate response”.

For each of the first five weeks, where daily measurements are recorded, the worst response will be used for analysis. Changes in ICPRE score over time (repeated measurement) will be analyzed using Generalized Linear Mixed Models.

H. Duration of treatment site pain response [Time Frame: Weekly week 1-9 after start of radiotherapy].

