Primary Ambulatory function	EQ-5D-5L mobility dimension	At nine weeks after start of radiotherapy	Ordinal	Wilcoxon rank-sum test
Severity of dysphagia, nausea, and dyspepsia	NCI-PRO-CTC-AE	Weekly, week 1-9 after start of radiotherapy	Ordinal, repeated measurement	Generalized Linear Mixed Models
Duration of dysphagia, nausea, and dyspepsia	NCI-PRO-CTC-AE	Within five weeks after start of RT (daily measurements) and at 6, 7, 8, and 9 weeks	Continuous, mean [range]	Descriptive graphical presentation and Wilcoxon rank-sum test for group comparison
Severity of cough, dyspnea, dyspepsia, dysphagia, hoarseness, oropharyngeal pain	NCI-CTC-AE	Weekly, week 1-5 after start of radiotherapy	Ordinal, repeated measurement	Generalized Linear Mixed Models
Duration of cough, dyspnea, dyspepsia, dysphagia, hoarseness, oropharyngeal pain	NCI-CTC-AE	Weekly, week 1-5 after start of radiotherapy	Continuous, mean [range]	Descriptive graphical presentation and Wilcoxon rank-sum test for group comparison
Pain response, severity	ICPRE score	Weekly, week 1-9 after start of radiotherapy	Ordinal, repeated measurement	Generalized Linear Mixed Models

Quality of life	EQ-5D-5L	Weekly, week 1-9 after start of radiotherapy	Categorical (index), and Visual analog scale (continuous)	As per described in EQ-5D-5L guidelines (7) Combined index is calculated using Denmark as reference. Changes in EQ-index value and VAS-score over time (repeated measurement) will be analyzed with Generalized Linear Mixed Models.
Quality of Life	EORTC-QLQ-C30	Weekly, week 1-9 after start of radiotherapy	Categorical (raw QLQ-C30 scores) and Continuous (the raw QLQ-C30 scores can be transformed to scores ranging from 0 to 100)	As per described in EORTC-QLQ-C30 guidelines (8). Descriptive statistics of QLQ-C30 domains and analysis of changes over time with Generalized Linear Mixed Models
Weight	Change in kg from baseline	Weekly, week 1-9 after start of radiotherapy	Continuous, repeated measurement	Linear Mixed Effects Models
Hospitalization rate	Days hospitalized of days alive (absolute numbers and %)	Week 1-9	Continuous, mean [range]	Wilcoxon rank-sum test
Re-irradiation rate, primary site	Number of patients receiving re-irradiation in each arm (absolute numbers and %)	3, 6- and 12-months after inclusion	Continuous, mean [range]	Wilcoxon rank-sum test

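### Analysis B models weekly peaks of daily scores (weeks 1-5) and single 24-hour scores (weeks 6-9) as one series, so modelled severity is expected to fall at week 6 even if symptoms do not change

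*SAP*

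**What the plan says.** Analysis B in the SAP has the window "Time Frame: Week 1-9 after start of radiotherapy (repeated measurement", and the analysis summary table repeats it as "Weekly, week 1-9 after start of radiotherapy", with the data type given as ordinal repeated measurement. The method is: "Changes in severity score over time (repeated measurement) will be analyzed using Generalized Linear Mixed Models". No link function, form of time or arm-by-time term is named.

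The value entered for weeks 1-5 is defined by "For each of the first five weeks, where daily measurements are recorded, the peak value will be used for analysis". No corresponding definition is given for weeks 6-9. The SAP's trial design section says the symptoms are "reported daily for 5 weeks and subsequently weekly for 4 weeks", and protocol section 4.2 and protocol Table 2 agree. The only PRO-CTCAE form supplied, in protocol Appendix A, asks: "In the last 24 hours, what was the SEVERITY of your DIFFICULTY SWALLOWING at its WORST". No form with a longer recall is given for the weekly phase.

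The opening of the SAP's Analysis section adds a completeness rule: "Primary analysis of NCI-PRO-CTC-AE toxicity will only include weeks where" three or more days were completed. It does not say how this rule works when only one form is due.

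**The concern.** The model treats nine weekly values as repeated measurements of one quantity, but they are two quantities. Up to week 5 each value is a maximum over several 24-hour periods: 3 to 7 if the completeness rule applies to Analysis B, 1 to 7 if it does not. From week 6 each value is one 24-hour period. A maximum over several readings is expected to exceed a single reading from the same distribution whenever the readings vary.

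The target of Analysis B is change over time, so a step created by the schedule falls in the result itself. Protocol section 1.2 reports that in the earlier prospective study toxicity came mainly in weeks 2 and 3. A drop at week 6 could then be read as a late phase of recovery that did not occur. A smooth or linear time term would also be misfitted.

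**Working it through.** The plan gives no figure for this model, so there is none to reproduce. The 62 patients per arm belongs to a different comparison.

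**Inputs from the documents.** Weeks 1-5: peak of daily scores (SAP, Analysis B). Weeks 6-9: one score per week (SAP, trial design; protocol section 4.2). Recall: 24 hours (protocol Appendix A). Scale: 0 to 4 (SAP, Analysis B). Minimum days: 3 (SAP, Analysis).

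**Assumptions, not in the documents.** The daily score is the number of cut-points 0.3, 1, 1.6 and 2.2 exceeded by a latent standard normal variable with within-patient day-to-day correlation ρ. The distribution is the same every day, so there is no true change over time.

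**Formula.** For a peak over k days, with Φ and φ the standard normal distribution and density functions,

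P(peak ≥ j) = 1 − ∫ Φ[(c_j − √ρ·u)/√(1−ρ)]^k φ(u) du,

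and the mean score is the sum of these probabilities over j = 1 to 4.

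**Single day (k = 1), any ρ.** 0.382 + 0.159 + 0.055 + 0.014 = 0.61.

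**Peak of 7, ρ = 0.7.** 0.686 + 0.386 + 0.171 + 0.054 = 1.30.

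| ρ | Mean, 1 day | Mean, peak of 3 | Mean, peak of 7 | Fall at week 6 (7 days completed) | Share scoring ≥1: peak of 7, then 1 day |
|---|---|---|---|---|---|
| 0.70 | 0.61 | 0.99 | 1.30 | 0.69 | 69%, then 38% |
| 0.85 | 0.61 | 0.87 | 1.07 | 0.46 | 59%, then 38% |
| 0.95 | 0.61 | 0.76 | 0.86 | 0.25 | 50%, then 38% |

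At ρ = 1 the fall is zero.

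**Other daily distributions (simulation, 400,000 patients, 7 days completed, ρ from 0.9 to 0.5).** With 70/18/8/3/1% on scores 0-4, the fall is 0.32 (0.79 to 0.47) to 0.84 (1.31 to 0.47). With 50/25/15/8/2%, it is 0.44 (1.31 to 0.87) to 1.08 (1.95 to 0.87). The direction is the same in every case; only the size depends on the assumptions.

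**Arm contrast.** Shift the latent score by −0.5 in one arm on every day.

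- Raw score scale: the difference in means is −0.31 on a single day, against −0.54 (ρ = 0.7) or −0.47 (ρ = 0.85) on a 7-day peak. A constant effect appears to shrink at week 6.
- Ordinal scale: the log odds ratio at the first cut-point is −0.83 on a single day, against −0.89 (ρ = 0.7) or −0.84 (ρ = 0.85) on a 7-day peak. The change is small.

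**Number of completed days.** With no treatment effect, the mean peak over 7 days exceeds that over 4 by 1.30 − 1.10 = 0.20 (ρ = 0.7) or 1.07 − 0.94 = 0.13 (ρ = 0.85).

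**The 3-day rule against the schedule.** One form is due per week in weeks 6-9, so no such week can reach three completed days. Applied literally to Analysis B, the rule leaves weeks 1-5 only and contradicts the stated week 1-9 window.

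**The case against.** The strongest reply is that the step is common to both arms. With equal completion and no treatment effect, it creates no arm difference. That stands. It does not rescue the time course, which is what Analysis B is set up to estimate and which the step distorts in both arms.

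Three stronger readings are tempting, and the documents do not support them.

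- *The arm-by-time effect is necessarily distorted.* This depends on the link, which the SAP does not name. The distortion is material on raw scores and small on an ordinal link, and the analysis summary does label the outcome ordinal.
- *The arm contrast is biased by unequal completion.* The weekly peak does rise with completed days, and the SAP's trial design section reports low compliance at the interim analysis. But nothing shows that completion differs by arm. Patients are blinded to allocation, and the SAP commits to reporting missing data by arm.
- *Sicker patients complete fewer days and so get lower peaks.* Neither document shows that they complete fewer days. Sicker patients may also score higher, so the net direction is unknown.

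It is also fair to say that the 3-day rule, if it covers Analysis B, narrows the dependence on completed days. And if it is applied literally, the two kinds of score are never joined, but only because weeks 6-9 disappear.

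**Conclusion.** The point holds for the time course. As written, Analysis B places an artificial fall at week 6. Under the latent-normal assumption it is about 0.25 to 0.69 points on a 0-4 scale for correlations of 0.95 down to 0.7 with seven completed days, and smaller with fewer days completed. The fall holds in expectation and needs only some day-to-day variation within a week. Its size rests on assumed score distributions and correlations.

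The consequence for the arm comparison is conditional on a raw-score model or on completion that differs by arm. The conflict between the 3-day rule and the week 1-9 window needs no assumption and has to be settled in any case.

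The scope is secondary. The co-primary peak uses weeks 1-5 only, so the week-6 step cannot affect it.

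**What to change.** Amend Analysis B and its row in the analysis summary before the data are analysed:

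1. Model weekly peaks for weeks 1-5 and single weekly scores for weeks 6-9 separately. Enter week as categorical, give arm contrasts within week, and name the link. State that the change from week 5 to week 6 will not be interpreted.
2. State that the 3-day rule applies to weeks 1-5 only.
3. Add a sensitivity analysis over weeks 1-9 using one score per week from a prespecified day, so that the summary is the same throughout.
4. Report the number of completed days per week by arm. Do not adjust for it: it arises after randomization, toxicity may affect it, and conditioning on it could itself bias the arm contrast.

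The cost is SAP wording, with no new data. The trial gives up a single pooled week 1-9 trend based on peak scores. The fixed-day analysis uses at most one of seven daily scores in weeks 1-5 and can miss short episodes (discomfort in the earlier study lasted 1 to 18 days), so it belongs as a sensitivity analysis and not as the main one.
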